### **9.2.1.3 Time to first PMR flare**

The duration to first PMR flare from clinical remission up to 52 weeks for each group will be analyzed.

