1.6 STATISTICAL MODIFICATIONS MADE IN THE STATISTICAL ANALYSIS PLAN

Due to the premature termination of the study, a total of 118 patients (42%) of the 280 patients planned were randomized. The randomized patients could continue in the study to complete the treatment period and the 6 weeks post-treatment follow up per protocol. Hence, there are no changes to the efficacy analysis plan per protocol.

The COVID-19 pandemic has also impacted data collection as patients may not be able to visit clinical sites for endpoint assessments. Additional patient level information at visits that were impacted by the pandemic situations were captured for assessments performed in visits that were delayed, not done, partially done on site, or partially done by phone. Major or critical COVID-19 impacted deviations per protocol were also recorded.

To assess the impact of the pandemic on the study, COVID-19 related summaries are added as below.

- a) Patients who permanently discontinue study treatment or study due to COVID-19 reasons will be summarized in patient disposition table
- b) Patient disposition by visit according to trial impact due to COVID-19
- c) Critical or major deviations summary according to COVID-19 impact
- d) Number (%) of patients experiencing at least one treatment-emergent COVID-19 related adverse event by primary SOC and PT

In addition, if > 10% patients are impacted by the COVID-19 pandemic, below summaries/analyses will be generated by COVID-19 impacted population (Yes, No):

- a) Extent of exposure to SC IMP
- b) Treatment compliance for SC IMP

- c) Number (%) of patients with TEAEs by primary SOC and PT, and
- d) Analysis of the primary endpoint of sustained remission at Week 52.

The population with and without trial impact (disruption) due to COVID-19 is defined in [Section 2.3.4](#).

In addition, upon meeting with Japan Health Authorities (PMDA) in April 2019, data for the components to calculate the PMR activity score (PMR-AS) were subsequently collected and the analysis plan is described in [Section 2.4.4.3](#).

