2.1.3.2 Secondary efficacy endpoint(s)

The following efficacy variables will be assessed:

- Components of sustained remission composite measure at Week 52
- Total cumulative corticosteroid (including prednisone) dose over during the treatment period
- Time to first PMR flare during the treatment period
- GTI Cumulative worsening score (CWS) and Aggregate improvement score (AIS) at Week 52.

Below are descriptions of these variables. Details related to imputation of GTI scores are described in [Section 2.5.2](#).

Components of sustained remission composite measure at Week 52

1. Proportion of patients who achieved disease remission by Week 12.
2. Proportion of patients who have no disease flare from Week 12 through Week 52.
3. Proportion of patients who have normalization of CRP (to <10 mg/L, with an absence of successive elevations to ≥ 10 mg/L) from Week 12 through Week 52.
4. Proportion of patients who successfully adhere to the prednisone taper from Week 12 through Week 52.

Total cumulative corticosteroid (including prednisone) dose during the treatment period

The total cumulative corticosteroid includes prednisone taper regimen per protocol, add-on prednisone prior to Week 12 or use of commercial prednisone during the study treatment period such as those employed to manage AE not related to PMR, and rescue corticosteroids dose prescribed for rescue therapy over the treatment period for PMR disease only.

Time to first PMR flare during the treatment period

The duration (in days) from randomization to first PMR flare after clinical remission and up to 52 weeks. Patients who never achieve remission will be censored at randomization day; and those who achieved clinical remission and never flared will be censored at the end of treatment assessment date up to Week 52.

The definition of PMR flare is provide in [Section 2.1.3.1](#) primary efficacy endpoint.

Clinical remission is defined as resolution of signs and symptoms and normalization of CRP (<10 mg/L). Intermittent missing CRP at visit will be imputed using last value carried forward (LOCF) approach. If missing signs and symptoms, then clinical remission is not achieved.

Glucocorticoid toxicity index (GTI) scores and components

The GTI is intended to capture glucocorticoid (GC)-related morbidity and GC-sparing ability of other therapies (2).

The GTI is composed of two components, the Composite GTI and the Specific List ([Table 2](#)).

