2.4.4.2 Analyses of secondary efficacy endpoint(s)

Components of sustained remission composite measure at Week 52

Descriptive statistics (i.e., counts and percentages) will be provided for the following binary variables by treatment groups:

- Patients who achieve disease remission by Week 12
- Patients who have absence of disease flare from Week 12 through Week 52
- Patients who have normalization of CRP (decrease to <10 mg/L) with sustained normalization from Week 12 through Week 52
- Patients who successfully adhere to the prednisone taper from Week 12 through Week 52

Total cumulative corticosteroid (including prednisone) dose

Descriptive statistics including the number of subjects, mean, and median of the total cumulative prednisone (or equivalent) dose will be presented for each treatment group. The difference between the medians and the corresponding 95% non-parametric confidence interval along with p-value from the non-parametric Wilcoxon rank-sum test between the treatment groups will also be provided.

Both expected and actual cumulative CS dose will be presented. The expected cumulative dose is based on CS tapering regimen up to end of treatment, assuming that the taper was continued without error while actual cumulative CS dose will be calculated as the total cumulative CS used for PMR disease up to the end of treatment, including expected prednisone in tapering regimen per protocol, add-on prednisone, CS used in rescue therapy and the use of commercial prednisone. Patients who received increased prednisone or equivalent in rescue therapy will be included in their original treatment groups.

In the scenario that a patient has already taken external CS for the disease before randomization on the day of randomization, the CS dose taken will be considered as the first dose of oral IMP. The first dose of prednisone per tapering regimen will be skipped, and the patient will take the second dose of prednisone on the next day.

Time to first PMR flare during the treatment period

Time (from randomization) to the first PMR flare after clinical remission up to Week 52 will be analyzed by Kaplan-Meier method providing the median, 25th and 75th percentiles (where possible) along with the 95% CI for the median. The comparison between the treatment groups will be performed using Cox proportional hazards model. Hazard ratio and the corresponding 95% CI and p-value will be provided.

Composite GTI and Specific List

GTI analyses

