Appendix D Summary of statistical analyses

Endpoint	Analysis		Statistical	Supportive	Subgroup	Other
	Population	Primary Analysis	Method	Analysis*	Analysis*	Analyses*
Primary Endpoint						
Patients who achieved sustained remission at Week 52	ITT	Proportion of patients achieving sustained remission at Week 52	Fisher's exact test	Tipping point analysis and primary endpoint excluding acute phase reactants and excluding incorrectly diagnosed PMR patients.	Yes Subgroups: Gender, race, region, age, baseline weight, BMI, baseline CRP, baseline ESR, baseline CS dose, prior relapse, COVID-19 impacted population.	No
Secondary Endpoints						
Patients who achieved of disease remission by Week 12	ITT	Proportion of patients who achieved of disease remission by Week 12	Descriptive	No	No	No
Patients who have absence of disease flare from Week 12 through Week 52	ITT	Proportion of patients who have absence of disease flare from Week 12 through Week 52	Descriptive	No	No	No
Patients who have normalization of CRP (decrease to <10 mg/L) with sustained normalization from Week 12 through Week 52	ITT	Proportion of patients who have normalization of CRP (decrease to <10 mg/L) with sustained normalization from Week 12 through Week 52	Descriptive	No	No	No
Patients who successfully adhere to the prednisone	ITT	Proportion of patients who successfully adhere to the prednisone taper from Week 12 through Week 52	Descriptive	No	No	No

	Analysis		Statistical	Supportive	Subgroup	Other
Endpoint	Population	Primary Analysis	Method	Analysis*	Analysis*	Analyses*
taper from Week 12 through Week 52						
Total cumulative prednisone (or equivalent) dose	ITT	Total cumulative prednisone (or equivalent) dose over 52-week treatment period	Wilcoxon rank-sum test	No	No	No
Time to the first PMR flare after clinical remission up to Week 52	ITT	Time (from randomization) to the first GCA flare after clinical remission up to Week 52	Kaplan-Meier estimates and Cox proportional hazards model	No	No	No
Total composite GTI total score	ITT	Cumulative GTI scores (CWS and AIS) at Week 52	Analysis of covariance (ANCOVA) model	No	No	Summaries of domain specific scores and specific list events at Week 12, 24, 40 and 52.
PMR activity score	ITT	PMR-AS at Week 52	MMRM model	No	No	Summaries of PMR-AS and components at baseline, Week 12, 24, and 52.
SF-36, EQ-5D-3L, FACIT-Fatigue, HAQ-DI, MD-VAS	ITT	Change from baseline at Week 52	MMRM model	No	No	No
Safety						

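### The SAP times first PMR flare from randomization but counts only post-remission flares, so without delayed entry the hazard ratio is biased whenever the arms reach remission at different times

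*SAP*

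**What the plan says.** Protocol 9.2.1.3: "The duration to first PMR flare from clinical remission up to 52 weeks for each group will be analyzed". The clock starts at remission.

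The SAP starts it at randomization in three places:
- The endpoint definition in 2.1.3.2: "The duration (in days) from randomization to first PMR flare after clinical remission and up to 52 weeks".
- The analysis in 2.4.4.2: "Time (from randomization) to the first PMR flare after clinical remission up to Week 52 will be analyzed by Kaplan-Meier method". The arms are then compared by a Cox model with a hazard ratio, 95% CI and p-value. Delayed entry is not mentioned.
- Appendix D: "Time (from randomization) to the first GCA flare after clinical remission up to Week 52". GCA appears here where PMR is evidently meant.

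On censoring, SAP 2.1.3.2 says "Patients who never achieve remission will be censored at randomization day". Remitters without a flare are followed until their treatment ends, at Week 52 at the latest, and censored then. Clinical remission in that section needs both resolution of signs and symptoms and CRP below 10 mg/L.

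SAP 1.5 lists only the sample size, significance level and confidence interval revisions. SAP 1.6 states "Hence, there are no changes to the efficacy analysis plan per protocol". Neither mentions a new time origin for this endpoint.

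**The concern.** The two documents define the same secondary endpoint on different clocks, and the SAP definition combines them. It keeps the protocol's condition that only a flare after remission is an event, but drops the matching origin. A patient who remits at Week 8 therefore contributes 8 weeks of follow-up in which an event is excluded by definition. That is immortal time, and it affects every patient who remits.

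The usual argument for a randomization origin, that it preserves the randomized comparison, does not help here. Patients who never remit are censored on day 0, so they never contribute time at risk.

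If both arms remit at the same pace, the immortal time is shared and the hazard ratio is hardly touched. If one arm remits later, it carries more event-free time by construction and looks better than it is. At stake are the hazard ratio, its interval and its nominal p-value.

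**Working it through.** **Plan's own figures.** The documents give no event count, hazard ratio or power for time to first flare. The only stated power is for the primary endpoint (59 per group, two-sided chi-square at 0.05, control rates 5/10/15%). It reproduces: 95.6/91.2/87.0% against 95.6/91.2/86.9% for 25 points, and 98.9/97.3/95.4% against 98.8/97.2/95.4% for 30 points. It has no bearing on this point.

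**Assumed inputs.** Flare hazards and remission times are not in the documents, so all values below are assumptions. Hazard ratios are sarilumab over placebo. Follow-up ends at Week 52.

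**Hand check.** Let the post-remission flare hazard be constant at h per week and remission occur at week R.
- Probability of a flare by Week 52: p = 1 - exp(-h(52 - R)).
- Mean time at risk from remission: p/h.
- Mean time counted under the SAP clock: p/h + R.
- Apparent rate under the SAP clock: p/(p/h + R).

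Take h = 0.0139 in both arms, so the true ratio is 1.
- R = 3.6: p = 0.490, counted time 35.2 + 3.6 = 38.8, rate 0.01261.
- R = 4.6: p = 0.483, counted time 34.7 + 4.6 = 39.3, rate 0.01227.
- R = 6.4: p = 0.469, counted time 33.8 + 6.4 = 40.2, rate 0.01169.
- R = 11.7: p = 0.429, counted time 30.9 + 11.7 = 42.6, rate 0.01008.

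With sarilumab at 3.6 weeks, the apparent ratio is 0.01261/0.01227 = 1.03 for a lag of 1 week, 0.01261/0.01169 = 1.08 for 2.8 weeks, and 0.01261/0.01008 = 1.25 for 8.1 weeks. Swapping the arms inverts the ratio.

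**Cox fits on simulated data** (8,000 per arm, remission detected at scheduled visits, placebo hazard 0.0139 per week):

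| True HR | Mean remission, sarilumab / placebo (weeks) | From remission | From randomization (SAP) | Randomization, entry at remission |
|---|---|---|---|---|
| 1.0 | 3.6 / 3.6 | 1.033 | 1.030 | 1.032 |
| 1.0 | 3.6 / 6.4 | 0.976 | 1.055 | 0.972 |
| 1.0 | 3.6 / 11.7 | 0.997 | 1.262 | 0.992 |
| 1.0 | 11.7 / 3.6 | 0.994 | 0.791 | 0.996 |
| 0.7 | 3.6 / 6.4 | 0.677 | 0.733 | 0.680 |
| 0.7 | 3.6 / 11.7 | 0.720 | 0.908 | 0.722 |
| 0.7 | 11.7 / 3.6 | 0.708 | 0.565 | 0.706 |

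Dividing the SAP column by the remission column gives the shift, for example 0.733/0.677 = 1.08 and 0.908/0.720 = 1.26. Over all settings run, including a hazard of 0.0277 and a true HR of 0.5, a lag of about 3 weeks moves the ratio 7-11% and a lag of about 8 weeks moves it 20-35%. The shift always favours the later-remitting arm.

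Other runs at a true HR of 1.0 gave 1.01-1.05 for a lag of about 1 week, 1.16-1.19 for about 4 weeks and about 1.30 for 7 weeks. One smaller set, with hazards of 0.02 and 0.04 per week, gave 1.31-1.42 for 8 weeks, so the upper end depends on the assumed flare rate.

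**If flare risk follows the taper week.** Both tapers are fixed by week since randomization (Protocol Appendix A). With a true HR of 0.70 and a hazard that changes with that week (0.005 to 0.02, or 0.03 to 0.01 per week), the fits ranged as follows:
- From remission: 0.515 to 0.917.
- From randomization as in the SAP: 0.431 to 1.098.
- From randomization with entry at remission: 0.657 to 0.724.

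Only the last stays near the truth under both kinds of hazard.

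**The case against.** The strongest reply is that the bias is conditional and may be small. That stands. Prednisone is identical in both arms for Weeks 0-3 (15, 15, 14, 12 mg) and higher on placebo from Week 4, and symptom resolution depends on it. Patients enter already on 7.5-20 mg/day. Inclusion criterion I 07 accepts a raised ESR or a raised CRP in the 12 weeks before screening, so some may start with CRP below 10 mg/L. A short lag is quite possible.

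A reader might infer that the hazard ratio is biased against sarilumab, because SAP 2.4.4.1 acknowledges the drug's effect on acute phase reactants and remission requires a normal CRP. The documents do not support that as a finding: they report no remission times, and the direction reverses if sarilumab remits later.

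A reader might also infer that restoring the protocol's clock is enough. It is not, because that clock is itself distorted when flare risk follows the taper week.

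The longer Kaplan-Meier median under the SAP is a consequence of its stated definition and not a bias. At an assumed 0.03 per week the median from remission is ln 2/0.03 = 23 weeks; from randomization it also includes the time to remission.

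Finally, the SAP 1.6 sentence is written about early termination, and SAP 1.5 describes amendment 02. They show that the change is not declared, and nothing about intent.

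**Conclusion.** The mismatch is certain: remission in Protocol 9.2.1.3, randomization in SAP 2.1.3.2, 2.4.4.2 and Appendix D, with no declaration. The mechanism is also certain: time in which no event is possible is counted as time at risk. The effect on the hazard ratio depends on a difference between arms in time to remission, which the documents do not let anyone estimate. On the assumed flare hazards it is essentially nil with equal remission times, a few percent at about 1 week, about 15-20% at about 4 weeks and about 20-35% at 7-8 weeks, in favour of the later-remitting arm.

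It would be wrong to read this as a threat to the trial's main result. SAP 2.4.4.4 places only cumulative corticosteroid dose after the primary endpoint, so the p-value for time to flare is nominal and the primary conclusion is unaffected. Either clock also conditions on remission after randomization, so neither gives a fully randomized comparison. How never-remitters are handled is a separate question.

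**What to change.** In SAP 2.1.3.2, 2.4.4.2 and Appendix D, keep randomization as the time scale and enter each patient into the Kaplan-Meier and Cox risk sets at the date of first clinical remission (left truncation). State how that date is derived from the visit records. Early risk sets may be small, so show numbers at risk.

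Reconcile the text with Protocol 9.2.1.3, declare and justify the change of origin in SAP 1.6, and report duration from remission to first flare as the protocol-defined descriptive summary. Correct GCA to PMR in Appendix D.

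The cost is one entry-time variable and one or two SAP sentences. No new data are needed.

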## **11.3 ANALYSIS POPULATIONS**

### **11.3.1 Efficacy populations**

#### ***11.3.1.1 Intent-to-treat /modified intent-to-treat population***

Intent-to-treat (ITT) population: all randomized population analyzed according to the treatment group allocated by randomization. All efficacy analyses will use this population.

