1.5 MODIFICATIONS TO THE STATISTICAL SECTION OF THE PROTOCOL

In general, the statistical methods remain unchanged by the protocol amendment 02 except for revisions made to sample size and power calculations as listed below:

Amended protocol 02 (19 April 2021):

As a result of the inability to recruit due to the COVID19 pandemic, the study was terminated prematurely resulting in a change in the total expected number of patients from 280 to 118 (Section 1.3).

- Statistical significance level changed from 0.01 to 0.05 due to the change in total expected number of patients.
- Power calculations revised due to the change in total expected sample size to 118, and the change in statistical significance level to 0.05.
- 99% confidence intervals revised to 95% confidence intervals associated with the change in statistical significance level to 0.05.

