Note that during the initial 12 weeks of prednisone taper, treatment for one flare before Week 12 is permitted if it can be successfully treated with a low dose (≤ 5 mg/day) prednisone add-on taper regimen (completed prior to Week 12) and provided that all other sustained remission parameters are met.

2. Absence of disease flare from Week 12 through Week 52.

Flare is defined as either 1) recurrence of signs and symptoms attributable to active PMR plus an increase in CS dose due to PMR, or 2) elevation of ESR attributable to active PMR plus an increase in CS dose due to PMR. Increase in CS dose is defined as:

- Any dose increase during the protocol defined steroid taper, or
- Re-initiation of prednisone therapy after the protocol defined taper has been completed.

Patients with disease flare are identified as those with the reason for treatment ticked “rescue therapy” in eCRF “Steroid Medication” page and to the question “If Rescue Therapy, please specify” ticked either “Active PMR” or “Elevated ESR Attributable to Active PMR”.

3. Sustained reduction of CRP (to <10 mg/L, with an absence of successive elevations to ≥10 mg/L) from Week 12 through Week 52

The status of normalization of CRP from Week 12 through Week 52 will be determined based on the CRP values measured at Week 16, Week 20, Week 24, Week 32, Week 40 and Week 52. If there are two or more consecutive visits with CRP ≥10 mg/L, then it is categorized as no normalization of CRP. Intermittent missing CRP at Week 16, Week 20, Week 24, Week 32, Week 40 or Week 52 will be imputed using last value carried forward (LOCF) approach up to the last non-missing measurement.

4. Successful adherence to the prednisone taper from Week 12 through Week 52

Successful adherence to the prednisone taper from Week 12 through Week 52 is defined as patients who did not take rescue therapy from Week 12 through Week 52 and any excess prednisone (beyond the per protocol CS tapering regimen) with a cumulative dose of ≤100 mg (or equivalent), such as those employed to manage AE not related to PMR. The cumulative dose of excess prednisone use will be counted from baseline to Week 52 (does not include add-on prednisone taken prior to Week 12).

In addition, patients who permanently withdraw from the study treatment prior to Week 52 will be considered as not having achieved component 2, 3, or 4 for the primary endpoint.

Blinding of CRP and ESR assessment results

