2.4.4 Analyses of efficacy endpoints

The primary and secondary efficacy endpoints will be analyzed using the ITT population. For patients who reduced dose to sarilumab 150mg during the course of the study, a listing of key efficacy endpoint variables will be provided.

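### Time to first flare censors never-remitters at day 0, so the hazard ratio labelled ITT compares remitters only and ignores rescues that come before or without remission

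*SAP*

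**What the plan says.** SAP 2.1.3.2 starts the clock at randomization and takes as the event the first flare after clinical remission, up to Week 52. Of the rest it says: "Patients who never achieve remission will be censored at randomization day". Remitters who never flare are censored at the end-of-treatment assessment. Remission means that signs and symptoms are gone and CRP is below 10 mg/L. It has no deadline, and missing signs and symptoms count as no remission.

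SAP 2.4.4.2 confirms the analysis: "Time (from randomization) to the first PMR flare after clinical remission up to Week 52 will be analyzed by Kaplan-Meier method", with a Cox hazard ratio, 95% CI and p-value. On the population, SAP 2.4.4 says "The primary and secondary efficacy endpoints will be analyzed using the ITT population", and Protocol 11.3.1.1 says of the ITT population "All efficacy analyses will use this population". Appendix D lists no supportive analysis for this endpoint.

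The protocol's definition differs. Section 9.2.1.3 reads "The duration to first PMR flare from clinical remission up to 52 weeks for each group will be analyzed", and section 11.4.2.2 names only study withdrawal as a reason for censoring. SAP 1.6, which lists modifications made in the SAP, does not mention the new time origin or the day-0 rule and says "Hence, there are no changes to the efficacy analysis plan per protocol".

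**The concern.** Three things are at stake.

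- **The comparison is selected after randomization.** Entry depends on an outcome that includes CRP. SAP 2.4.4.1 plans a sensitivity analysis of the primary endpoint without acute phase reactants, precisely because sarilumab acts on them. Time to flare has no such safeguard.
- **Real events are dropped.** SAP 2.1.3.1 finds flares from a steroid-page field ("Patients with disease flare are identified as those with the reason for treatment ticked" as rescue therapy, for active PMR or an attributable ESR rise). A patient who carries that flag but never remits, or whose only rescue comes before a later remission, contributes no event. In the primary endpoint, rescue for active PMR before Week 12 is a failure. The taper schedules diverge from Week 4 (10 versus 12 mg/day) and stand at 3 versus 9 mg/day in Week 11, so early rescue could well differ by arm.
- **The clock has moved.** Counting from randomization gives every remitter a stretch before remission in which no event can be recorded. If one arm remits earlier, that alone shifts the hazard ratio.

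**Working it through.** The documents give no figure for this endpoint to reproduce. The power table in SAP 1.3 concerns the primary endpoint only.

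**Step 1: day-0 censoring equals deletion.** Each event at time s contributes exp(βg_i) / Σ exp(βg_j) to the Cox partial likelihood, where the sum runs over patients with t_j ≥ s. A patient with t_j = 0 is in that sum for no s > 0. In Cox fits with 59 per arm and 10% to 40% never-remitters per arm, estimates with these patients censored at day 0 and with them deleted were identical (maximum difference 0). If 20% never remit in each arm, 0.2 × 59 ≈ 12 per arm, so 24 of 118 randomized patients carry no information.

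**Step 2: size of the bias.** All inputs here are assumed, since the documents give none:

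- True effect on first rescue: none (HR 1.00).
- Rescue by Week 52: 40% in each arm, so 0.40 × 118 ≈ 47 first rescues.
- Severity: standard normal; the rescue hazard is multiplied by 2.7 per SD.
- Remission: correlation rho between severity and non-remission; remission at day 15, 29, 57 or 85 with probability 25% each.
- SAP rule: never-remitters deleted; a rescue before remission is not counted and the patient is followed to day 364.

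| Remission, placebo / sarilumab | rho 0.3 | rho 0.6 | rho 0.9 |
|---|---|---|---|
| 95% / 95% | 1.00 | 1.00 | 1.00 |
| 90% / 95% | 1.01 | 1.04 | 1.07 |
| 80% / 90% | 1.04 | 1.07 | 1.14 |
| 60% / 80% | 1.07 | 1.15 | 1.28 |
| 50% / 70% | 1.06 | 1.16 | 1.29 |
| 80% / 60% | 0.93 | 0.86 | 0.78 |
| 60% / 80%, severity ×1.65 per SD | 1.03 | 1.08 | 1.14 |

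At rho 0 the rule gives 0.99 to 1.01 throughout. Time to first rescue in all randomized patients also gives 0.99 to 1.01 in every case. If the arms differ only through CRP (symptoms resolved in 80% of both; CRP normal in 75% on placebo and 100% on sarilumab), the SAP-rule HR is 1.00 at rho 0 and roughly 1.1 to 1.2 at rho 0.3 to 0.9. Repeat runs agree to within about 0.02.

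**Step 3: lost events and precision (rho 0.6).** With 1:1 allocation the SE of the log hazard ratio is roughly 2/√events.

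- All randomized: 47 events, 2/√47 = 0.29.
- 80% / 90%: about 18 uncounted, 29 left, 2/√29 = 0.37 (simulated 0.38).
- 60% / 80%: about 25 uncounted, 22 left, 2/√22 = 0.43 (simulated 0.44).

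If early rescue is rarer, the uncounted numbers fall to 13 and 21.

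**Step 4: time origin alone.** Give both arms the same flare hazard after remission, and let sarilumab patients remit earlier. Timed from remission, the HR is 1.00. Timed from randomization, it is about 1.03 for a mild shift (10%-20%-30%-style probabilities only slightly reordered: 0.2/0.25/0.25/0.3 on placebo versus the reverse), 1.07 for a moderate shift and 1.09 for a full reversal (0.1/0.2/0.3/0.4 versus the reverse). If placebo patients remit earlier it is about 0.91. These values move slightly with the flare rate assumed.

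**The case against.** The strongest reply is that conditioning on remission is the protocol's own choice. Flare is defined as recurrence, and a patient who never remits cannot recur. That stands: flare after remission is a legitimate question. It does not justify calling the answer an ITT comparison. Never-remitters remain in the displayed N, but they contribute nothing to the estimate.

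Other points stand in part.

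- **Rescues are reported elsewhere in all randomized patients:** in the disposition table (SAP 2.2), in components 1 and 4 of the primary endpoint, and in cumulative steroid dose, the only secondary endpoint in the testing sequence (SAP 2.4.4.4). What is missing is a between-arm comparison of their timing. Component 1 does not give the number dropped either: it uses the last assessment up to Week 12, while remission here has no deadline and a different missing-data rule.
- **The missing-symptoms rule probably works visit by visit**, so one missed assessment does not make a never-remitter if another visit qualifies.
- **The no-change statements are narrower than they look.** SAP 1.5 ("the statistical methods remain unchanged by the protocol amendment 02 except for revisions made to sample size and power calculations") covers the amendment only, and the sentence in SAP 1.6 follows from early termination. Even so, the new time origin is declared nowhere. Starting at remission has its own drawback, a time zero that is not randomized, so either choice needs stating.
- **The bias is small against the noise.** On the log scale, ln 1.07 = 0.07 against SE 0.38, and ln 1.15 = 0.14 against SE 0.44, or 0.2 to 0.3 SE. If sarilumab patients remit more often, the modelled bias runs against sarilumab.
- **First rescue is not a perfect substitute.** Early flares treated with the permitted add-on prednisone may not carry the rescue tick.

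**Conclusion.** The concern holds: the rule is wrong as written. The reported hazard ratio is a comparison among remitters, selected partly on CRP, under an ITT label and with a time origin that differs from the protocol without being declared.

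Bias needs two conditions together: remission rates that differ by arm, and a link between failing to remit and flare risk. Under the assumed rates that favour sarilumab for remission, a true HR of 1.00 appears as 1.01 to 1.29; with remission 80% on placebo and 60% on sarilumab it appears as 0.78 to 0.93. Without either condition there is no selection bias. Events are still lost: even at 95% remission in both arms, about 12 of 47 first rescues go uncounted.

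The consequences are limited. Never-remitters are already non-responders in the primary endpoint, and this p-value is nominal. The analysis should be corrected, but the trial's main conclusion does not depend on it.

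**What to change.** 1. **Add one analysis of all randomized patients:** time from randomization to the first rescue steroid for active PMR or an attributable ESR rise, whether or not remission came first. Censor the rest at their last assessment up to Week 52, including the visits after stopping treatment that Protocol 10.4.4 asks sites to collect. Call it first rescue rather than flare, and state how early flares treated with add-on prednisone are counted. Repeat it with the active-PMR tick alone, to match the sensitivity analysis without acute phase reactants. If a composite of flare or no remission by Week 12 is also shown, give a version without CRP and ESR and note that events will tie at Week 12.
2. **Keep the existing analysis, but label it as among remitters.** Align its time origin with Protocol 9.2.1.3 or declare the change in SAP 1.6. Report never-remitters by arm, separating those with missing signs and symptoms.

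The cost is one derivation from a field already used for component 2, one row in Appendix D and a label change; no new data are needed. The existing Appendix D row needs editing anyway, because it names GCA flare instead of PMR flare. The drawbacks are that first rescue overlaps components 2 and 4 of the primary endpoint and depends on the investigator's decision to treat.
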